Title: Water Exchange Colonoscopy Decreased Adenoma Miss Rates in the Right and Proximal Colon: An Observational Study Using A Tandem Colonoscopy Approach

NCT Number: NCT03832322

Unique Protocol ID: EGH-2018

Date: Jan 3, 2019

STUDY PROTOCOL

BACKGROUND

Colonoscopy is currently regarded as the gold standard to detect and prevent colorectal cancer (CRC). It is widely practiced and generally safe and accurate, but not perfect. A substantial number of neoplastic lesions were missed according to back-to-back (tandem) air insufflation colonoscopy studies. In a systematic review of tandem colonoscopy studies, a 22% pooled miss-rate for adenomas were reported. Of all post-colonoscopy CRCs (PCCRCs), 58% were attributed to lesions missed during examination. Colonoscopy maneuvers helping to reduce AMR, particularly in the proximal and right colon, have the potential to decrease the incidence of PCCRCs.

Water exchange (WE) colonoscopy is characterized by the gasless insertion to the cecum in clear water and maximizing cleanliness during insertion. WE colonoscopy has been shown to improve the overall adenoma detection rate (ADR), compared to air insufflation colonoscopy. The impact of optimal WE with near-complete removal of infused water on proximal and right colon AMR has not been reported.

The primary outcomes of this study were the right and proximal colon AMRs determined by tandem colonoscopy using WE or CO₂ insufflation for screening and surveillance indications. The secondary outcomes were the combined right and proximal colon AMR and hyperplastic polyp miss rate (HPMR), overall ADR and other adenoma detection related metrics between the two colonoscopy methods.

METHODS

This was an observational study comparing consecutive group of WE and CO₂ insufflation in terms of right and proximal colon AMR by tandem colonoscopy. Consecutive patients were enrolled from July 2018 to November 2018 at Evergreen General Hospital, Taoyuan, Taiwan.

Participants

Consecutive patients aged 20 years or older undergoing colonoscopy for screening and surveillance indications were considered for enrollment. Exclusion criteria included familial adenomatous polyposis and hereditary non-polyposis CRC syndrome, personal history of inflammatory bowel disease, previous colonic resection, inability to achieve cecal intubation, obstructive lesions of the colon, poor colon preparation, inability to completely remove a polyp, gastrointestinal bleeding, allergy to fentanyl or midazolam, American Society of Anesthesiology classification of

physical status grade 3 or higher, mental retardation, pregnancy, and refusal to provide a written informed consent.

Bowel Preparation and Sedation

Patients were instructed to eat low-residual foods for two days before colonoscopy. All patients received a split dose of 3-L polyethylene glycol (Klean-Prep) for bowel preparation. Colonoscopy were performed with moderate sedation (intravenous fentanyl plus midazolam) administered by the colonoscopist.

First-pass Colonoscopy Procedure

Colonoscopies are performed by two board-certified colonoscopists ([name], [name]) using a standard colonoscopy (CF-Q260AL/I; Olympus Medical Systems Corp., Tokyo, Japan). [name] was involved in the study design, data analyses, and report preparation, but not in patient enrollment. Colonoscopy began with the patients in the left lateral position. In the WE group, the air pump was turned off before starting the procedure. During the insertion phase, air and residual water or feces in the rectum were aspirated, and then the colon was irrigated with water using flushing pumps (Olympus AFU-100; Olympus Corp.). There was no restriction placed on the overall volume of water infused to achieve adequate cleansing. WE entailed the infusion of water to open the lumen and sequential suction of water. Air pockets, when encountered, was aspirated. When the cecum was reached and after most of the water was suctioned to collapse the cecal lumen, CO2 was opened. In the CO2 group, colonoscopy was performed in the usual fashion, with minimal insufflation required to aid insertion. Cleaning in the CO2 group was predominantly performed during withdrawal. Polyp resection was done during insertion and withdrawal in both groups.

Second-pass Colonoscopy Procedure

After the first complete withdrawal of the colonoscope, a second colonoscopic examination aided by CO2 insufflation during insertion and withdrawal was performed by the same endoscopist. In both groups, the colonoscope was reinserted into the cecum as quickly as possible, and the entire colon was re-examined. Polyp resection was carried out during insertion and withdrawal in both groups during the second-pass examination. All polyps identified in the second-pass examination were defined as missed polyps with the exception of the diminutive polyps in the rectosigmoid colon that remain after the first-pass colonoscopy.

Definition

Complete colonoscopy was defined as successful cecal intubation. Insertion time was defined as the time between the scope insertion and cecal intubation. Withdrawal time was defined as the time from cecal intubation to the time when the colonoscope was withdrawn from the anus, including the time taken for mucosal cleaning and polypectomy. Total procedure time was the sum of insertion time and withdrawal time. A Poor colon preparation was defined as a total BBPS score of 5 or less.

All colonic polyps removed during procedures were sent for histological examination with clear labeling of location and sequences of colonoscopy. The location of colonic polyps was defined according to the anatomical distribution. Right colon was defined as cecum, ascending colon, and hepatic flexure. Proximal colon was defined as right and transverse colon. Diminutive polyps were defined as polyps with size ≤ 5 mm. Small polyps were defined as polyps with size 6-9 mm. Large polyps were defined as polyps with size ≥ 10 mm. Adenomas included all adenomas and sessile serrated adenoma. Advanced adenomas were defined as those lesions with one of the following criteria: 1) lesions larger than 10 mm in diameter; 2) lesions with a villous component; 3) lesions with high-grade dysplasia; and 4) lesions with invasive features.

Lesions detected on the first-pass examination were used for the calculation of adenoma detection. ADR was defined as the proportion of colonoscopies where at least one adenoma was found. Proximal hyperplastic polyp detection rate (PHP-DR) was defined as the proportion of patients undergoing colonoscopy in whom at least one hyperplastic polyp was identified in the proximal colon.

Lesions detected on the second-pass examination were used for the calculation of adenoma or polyp miss. AMR and HPMR were calculated as the number of adenomas and hyperplastic polyps missed in the first colonoscopy divided by the total number of adenoma and hyperplastic polyps detected during both the first and second colonoscopies.

STATISTICAL ANALYSIS PLAN

Sample size estimation

The sample size estimation was based on the assumption that WE colonoscopy reduced proximal colon AMR compared to conventional CO2 insufflation colonoscopy. We estimated the proximal colon AMR in the CO2 group to be 30% and the average detected number of proximal colon adenoma to be 0.9 per subject after first colon examination. To show a clinically important improvement of proximal colon AMR reduction by the WE colonoscopy, we assumed that WE colonoscopy should reduce the AMR by 18%. With a statistical power of 80% and a two-side significance level of 0.05, 82 patients were needed in each study arm.

Statistical analysis

Summary statistics were presented as frequencies and percentages in the case of categorical variables and as the means with standard deviations (SD) in the case of continuous variables. Student's *t*-test for continuous factors, Wilcoxon rank sum test for ordinal variables (such as polyp size), and Chi-square test for categorical variables were used to assess differences in demographic and clinical characteristics of patients in each group. All statistical analyses were performed by using SAS version 9.3 or later (SAS Institute Inc., Cary, NC, USA). The criterion for statistical significance will be *P* value <0.05.

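### The WE versus CO2 comparison is non-randomised with no stated assignment rule, and the SAP offers only unadjusted tests; add a small adjusted AMR and ADR analysis, labelled post hoc, beside the crude one

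*Combined protocol and SAP*

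**What the plan says.** **Design.** The Methods section states: "This was an observational study comparing consecutive group of WE" and CO2 insufflation. Enrolment was consecutive at one hospital from July to November 2018. Randomisation is not mentioned, and no section says whether calendar time, endoscopist, patient choice or something else decided the method.

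**Who is pooled.** First-pass Colonoscopy Procedure: "Colonoscopies are performed by two board-certified colonoscopists", with no split by method. Participants: those "undergoing colonoscopy for screening and surveillance indications were considered for enrollment", aged 20 or older.

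**What is held constant.** The preparation was uniform ("All patients received a split dose of 3-L polyethylene glycol (Klean-Prep) for bowel preparation"), as was the colonoscope. After the first pass, "a second colonoscopic examination aided by CO2 insufflation during insertion and withdrawal was performed by the same endoscopist".

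**Outcomes.** Right and proximal colon AMR are primary; overall ADR is secondary. AMR is counted per lesion (missed adenomas over adenomas found on both passes). ADR is counted per colonoscopy from first-pass lesions only.

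**Analysis.** The Statistical analysis section lists three procedures and ties them to patient characteristics: "Chi-square test for categorical variables were used to assess differences in demographic and clinical characteristics of patients in each group". The other two are Student's t-test and, with an example that concerns lesions rather than patients, the "Wilcoxon rank sum test for ordinal variables (such as polyp size"). It names no model, covariate, matching, weighting or stratification.

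**Timing.** The document is dated 3 January 2019, after enrolment ended, and its title already states the result.

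**The concern.** The study is openly observational, so the lack of randomisation is not itself the defect. The defect is that the route into each group is unstated and no analysis step deals with the consequences.

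The tandem design controls part of the problem. AMR is a ratio within the same patients, so differences in adenoma burden matter less for it than for ADR, which depends directly on burden and takes nothing from the second pass. But WE is still compared with CO2 between different patients. A difference in endoscopist, indication, age, sex or period that relates to missing or finding adenomas passes straight into the contrast. One site, a five-month window and uniform preparation limit this; they do not balance those factors between groups.

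The listed tests are tied to patient characteristics. The polyp-size example suggests they may extend to lesions, but none is expressly assigned to AMR and none is adjusted. A lesion-level test would also ignore that one patient can contribute several adenomas.

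At stake are the size of the AMR and ADR differences and their P values. If each endoscopist used one method, or the groups were separate time blocks, the WE effect could not be separated from operator or period at all.

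**Working it through.** **Inputs from the SAP (Sample size estimation).** Proximal AMR 30% with CO2; "we assumed that WE colonoscopy should reduce the AMR by 18" percent, read here as absolute points (30% to 12%); 0.9 proximal adenomas per subject; 82 patients per arm; 80% power; two-sided 0.05.

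**The plan's own figure.** Two proportions, 0.30 vs 0.12, pooled variance: 80 lesions per arm, and 80/0.9 = 89 patients. Unpooled: 77 lesions, 86 patients. The stated 82 is not reproduced. That is a separate matter and does not affect this point. A relative 18% (30% to 24.6%) would need more than 1,000 lesions per arm, which supports the absolute reading.

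**Adenomas per arm (taken as equal).** 82 × 0.9 = 73.8 if 0.9 is the total; 82 × 0.9/0.70 = 105.4 if 0.9 is the CO2 first-pass count.

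**Bias from one confounder (illustration; gaps and shares assumed).** Bias = AMR gap between endoscopists × difference in endoscopist share between groups.

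| Share difference | Gap 10 points | Gap 20 points |
|---|---|---|
| 10 points | 1 | 2 |
| 20 points | 2 | 4 |
| 40 points | 4 | 8 |

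To create all 18 points alone, endoscopist would need a gap of 0.18/0.40 = 45 points at a 40-point share difference, or 0.18/1.0 = 18 points under full aliasing.

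**False rejection under a true null.** With bias b and mean AMR m, the group AMRs are m ± b/2. SE = √[sum of p(1−p) / n]; rejection ≈ Φ((b − 1.96·SE₀)/SE) plus a negligible opposite tail, where SE₀ is pooled or unpooled. Example: b = 0.08, m = 0.21, n = 105.4 gives SE = √[(0.1411 + 0.1875)/105.4] = 0.0558, and Φ(1.433 − 1.96) = 0.299. Over n = 73.8 or 105.4 and m = 0.21 or 0.30:
- b = 0.02: 0.058-0.065
- b = 0.04: 0.083-0.110
- b = 0.08: 0.184-0.299

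**Simulation (1,500 runs per setting; 82 patients per arm; negative binomial lesion counts with mean 0.9).** The null runs use an assumed binary confounder with miss rates of 15% vs 30%. The power runs use 30% vs 12% and a covariate that has no effect. Adjustment is logistic regression on group and the covariate, with patient-clustered errors.

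| Split between groups | Type I, crude | Type I, adjusted | Power, crude | Power, adjusted |
|---|---|---|---|---|
| 50/50 | 5.7% | 5.3% | 78% | 76% |
| 60/40 | 7.5% | 5.1% | 78% | 74% |
| 70/30 | 15.5% | 5.6% | 79% | 70% |
| 80/20 | 27.1% | 7.0% | 78% | 58% |

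**Would the baseline tests catch it?** For a 40% vs 60% endoscopist split at 82 per arm: (0.20 − 1.96·√(0.50/82))/√(0.48/82) = 0.61, so power is 73%. Only adenoma-bearing patients contribute to AMR. If counts are Poisson (assumed), they number 82 × (1 − e^−0.9) = 48.7 to 82 × (1 − e^−1.286) = 59.3 per arm, and power falls to 51-59%. Overdispersion would leave fewer.

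**Events available for a model.** Missed proximal adenomas: 73.8 × 0.42 = 31.0 to 105.4 × 0.42 = 44.3. With 5-6 parameters that is 31.0/6 = 5.2 to 44.3/5 = 8.9 per parameter.

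**Precision cost.** If covariates explain R² = 0.05-0.30 of group (assumed; linear-model approximation), variance rises by 1/(1 − R²) = 1.05-1.43 and interval width by 1.03-1.20. The half-width for 30% vs 12% is 1.96·√(0.3156/73.8) = 12.8 points, rising to 13.2-15.3; with 105.4 adenomas it is 10.7, rising to 11.0-12.8. Clustering is ignored here.

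**The case against.** **The harm is hypothetical.** No imbalance is documented, and moderate endoscopist imbalance alone would not produce 18 points. This stands: what is shown is exposure to bias, not a biased estimate.

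**The illustration is generous.** A weak endoscopist also misses on the second pass, which compresses AMR differences. If the two passes are independent and equally sensitive (an assumption), AMR = m/(1 + m), where m is the per-pass miss rate. A 10-point AMR gap centred on 21-30% then needs a 16-21 point gap in m, and a 20-point gap needs 33-42 points. That is a lot for two board-certified colonoscopists at one site. The 18-30% figure needs the top of both assumed ranges at once, so it is an upper illustration. Endoscopist is also only one of several candidate confounders.

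**Too few events for the covariates named.** Partly right for an outcome regression: group plus five single-term covariates is six parameters, and month in categories would add more. A patient-level propensity score avoids this, because it is fitted on 164 patients rather than on 31-44 missed lesions.

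**Adjustment may be impossible.** If the groups were sequential blocks, period cannot be adjusted for. Correct, which is why the assignment rule must be stated first.

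**The plan already compares baseline characteristics.** That can show imbalance in what was recorded, with limited power. It corrects nothing.

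**It is too late to prespecify.** True; the analysis can carry only post hoc weight.

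**Conclusion.** The point holds. The comparison is non-randomised, the assignment rule is absent, and the only tests named are unadjusted. The size of any bias cannot be computed, since the documents give neither AMR by endoscopist nor the split by group. Under the assumed gaps and imbalances, bias ranges from none (balanced) to 8 points. That is short of the planned 18, but enough at the upper end to distort the P value materially. Full aliasing of group with endoscopist or period is neither stated nor excluded; it is the one case in which the WE effect could not be separated from that factor.

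This is a change the sponsor should make: the gap in the text is certain, its effect on the estimate is unknown, and the remedy is cheap. Adjustment will not remove unmeasured confounding.

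**What to change.** 1. State how patients came to receive WE or CO2, and tabulate group by endoscopist and by month. If group is aliased with either, say that the WE effect cannot be separated from it.
2. Where the groups overlap, add an adjusted comparison of proximal and right colon AMR at lesion level and of ADR at patient level. Use pre-procedure factors as far as recorded: endoscopist, indication, age, sex and calendar period.
3. Keep it small: one patient-level propensity score used for weighting, or a regression with few terms. Right colon AMR will have fewer events than the 31-44 expected proximally.
4. Use patient-clustered standard errors for AMR. This handles several adenomas per patient and is separate from confounding.
5. Check balance by standardised differences among the adenoma-bearing patients, not only among all 164.
6. Do not adjust for bowel cleanliness or withdrawal time, through which WE may act.
7. Report the adjusted result beside the crude one as a post hoc sensitivity analysis.

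**Cost.** SAP wording, one table and analysis time. No new patients are needed if the covariates were recorded; the documents do not list the data fields, so this must be checked. Under the assumed R² of 0.05-0.30, intervals widen by about 3-20%, equivalent to about 5-43% more patients for the same precision; weighting may cost more or less.

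### No test or unit of analysis is assigned to the primary adenoma miss rates, and the only listed test that fits them ignores clustering of adenomas within patients

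*Combined protocol and SAP*

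**What the plan says.** The Background section fixes the endpoints: "The primary outcomes of this study were the right and proximal colon AMRs determined by tandem colonoscopy". The Definition section gives the formula: "AMR and HPMR were calculated as the number of adenomas and hyperplastic polyps missed in the first colonoscopy divided by the total number", the denominator being the "total number of adenoma and hyperplastic polyps detected during both the first and second colonoscopies". Numerator and denominator both count lesions, and no per-patient miss rate is defined. By contrast, the adenoma detection rate (ADR) is a per-examination outcome: "ADR was defined as the proportion of colonoscopies where at least one adenoma was found".

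The technique is set once per patient, for the whole first-pass examination (First-pass Colonoscopy Procedure), and the groups are not randomised: "This was an observational study comparing consecutive group of WE".

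The Statistical analysis section lists the t-test, the Wilcoxon rank sum test and chi-square, which "were used to assess differences in demographic and clinical characteristics of patients in each group". One example points below patient level: "Wilcoxon rank sum test for ordinal variables (such as polyp size), and Chi-square test for categorical variables were used". The section gives AMR no test, model, confidence interval or unit of analysis, and nothing in the document deals with several lesions from one patient.

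**The concern.** The test behind the main conclusion is left open. If the list is meant to reach the miss rates, chi-square is the candidate, because missed or not missed is a categorical result. A t-test or Wilcoxon test would need a miss rate for each patient. The plan does not define one, and it does not exist for a patient without adenomas.

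A chi-square test on adenomas counts each as an independent observation. Adenomas in one patient share the same bowel preparation, the same cleansing and the same examiner, so positive correlation of misses is plausible, although the documents give no value. With positive correlation the chi-square variance is too small on average, and the test declares a WE effect too often when there is none. Both primary outcomes are exposed, as are the hyperplastic polyp miss rate (HPMR) and polyp size if it is compared lesion by lesion.

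**Working it through.** **Inputs from Sample size estimation.** CO2 proximal AMR 0.30; reduction 18%; 0.9 proximal adenomas per subject; 80% power; two-sided 0.05; 82 patients per arm. I read the 18% as absolute (0.30 to 0.12). The relative reading, 0.30 × 0.82 = 0.246, needs 1,068 lesions per arm and cannot lie behind 82.

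**Assumed, not in the documents.** ICC of misses within a patient 0.05 to 0.30. Adenoma counts Poisson, or negative binomial with k = 1 or k = 0.5. The 0.9 is used as the total count and also as a first-pass count, which gives a total of 0.9/0.7 = 1.29.

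**The plan's own figure.** The usual two-proportion formula is n = [1.96√(2 × 0.21 × 0.79) + 0.842√(0.30 × 0.70 + 0.12 × 0.88)]² / 0.18², which rounds up to 80 per arm. This is close to 82 if each patient supplies one unit. Using the 0.9 gives 80/0.9 = 89. A one-sided, continuity-corrected calculation gives 73/0.9, which rounds up to 82, but it contradicts the stated two-sided level. Each of these treats the units as independent.

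**Multiple adenomas.** With Poisson counts and mean 0.9, the share of patients with two or more is 1 − e^(−0.9)(1 + 0.9) = 0.23.

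**Design effect.** DE = 1 + (E[m²]/E[m] − 1) × ICC, where m is the number of adenomas per patient. The bracket equals the mean for Poisson counts and mean × (1 + 1/k) for the negative binomial.
- Mean 0.9: from 1 + 0.9 × 0.1 = 1.09 (Poisson, ICC 0.1) to 1 + 2.7 × 0.3 = 1.81 (k = 0.5, ICC 0.3).
- Mean 1.29: from 1.13 to 1 + 3.857 × 0.3 = 2.16 on the same settings.

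The large-sample alpha is 2[1 − Φ(1.96/√DE)]: 0.061 at DE 1.09 and 0.145 at DE 1.81.

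**Simulation.** Beta-binomial misses, 82 patients per arm, AMR 0.30 in both arms, 40,000 replicates. Rejection rate of a nominal 5% lesion-level chi-square:

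| Mean | Counts | ICC 0 | 0.05 | 0.1 | 0.2 | 0.3 |
|---|---|---|---|---|---|---|
| 0.9 | Poisson | 0.051 | 0.055 | 0.061 | 0.072 | 0.082 |
| 0.9 | k = 1 | 0.050 | 0.060 | 0.073 | 0.092 | 0.114 |
| 0.9 | k = 0.5 | 0.051 | 0.065 | 0.083 | 0.114 | 0.146 |
| 1.29 | Poisson | 0.050 | 0.059 | 0.065 | 0.080 | 0.098 |
| 1.29 | k = 1 | 0.050 | 0.064 | 0.080 | 0.112 | 0.141 |
| 1.29 | k = 0.5 | 0.050 | 0.072 | 0.096 | 0.139 | 0.181 |

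A patient-clustered score test with independence weights stayed at 0.049-0.054 in all these cells. In a separate, smaller simulation over similar settings, a plain Wald test with a cluster-robust variance ran at 0.050-0.069, hence the preference for a score test or a small-sample correction.

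**Right colon.** No right-colon count is given, so no figure can be computed. Since "Proximal colon was defined as right and transverse colon", its mean count cannot exceed the proximal one, and by the design-effect formula its inflation is no greater at the same ICC and k.

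**The case against.** The strongest reply is that the text shows an omission, not an error. A reader might infer that chi-square was, or will be, applied to adenomas. The documents do not say so: the test list is tied to patient characteristics, and the polyp-size example only suggests a wider reach. That stands, and the inflated alpha follows only if the gap is filled in that way. Likewise, pooling is an inference. The formula divides a count by a count without saying over whom it is summed, and a sample size counted in patients adds to the ambiguity. Pooling is still the natural reading, because a per-patient ratio is undefined without adenomas.

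A reader might also infer that P values here are too small and that clustering must raise them. Inflation is a property over repeated studies. In null simulations on these settings the clustered variance was smaller than the chi-square variance in about 27-39% of datasets at ICC 0.05 and 11-27% at ICC 0.1, but in only 0-3% at ICC 0.3.

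The largest figures need k = 0.5 and ICC 0.3 together. The Participants section excludes two hereditary syndromes, which removes some patients likely to have extreme counts but does not rule out overdispersion.

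Finally, power at mean 0.9 is already 0.75-0.77 at ICC 0. A reader might blame clustering for that, but with no correlation it is a separate sample-size matter.

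**Conclusion.** The concern holds as a gap in the plan. The primary AMRs have no assigned test or unit, and the one listed test that fits their ratio is anti-conservative over repeated studies under positive within-patient correlation. How far is not known from the documents. It is modest with Poisson counts and low ICC (alpha about 0.055-0.065 at ICC 0.05-0.1), material with Poisson counts at ICC 0.3 (about 0.08-0.10), and large (about 0.15-0.18) only with k = 0.5 and ICC 0.3. At ICC 0 there is no inflation. I am confident about the omission and the direction of the error, much less so about its size. It should be fixed, but it does not show that the trial's conclusion is wrong.

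**What to change.** State the unit of analysis for right and proximal AMR. Compare them, and HPMR, and polyp size if compared per lesion, with a patient-clustered method. For the miss rates it should keep the pooled ratio. One option is a GEE with independence working correlation, patient as cluster, and a score test or small-sample-corrected robust standard errors. Report the AMR difference with a cluster-robust 95% CI. Keep chi-square for patient-level outcomes such as ADR.

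Enrolment ended in November 2018 and the document is dated January 2019. The change therefore belongs in the analysis and its reporting. The report should say which test and unit were used and label the clustered analysis as not prespecified before data collection.

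**Cost.** A few lines in SAS, the named software (for example PROC GENMOD with REPEATED SUBJECT=patient / TYPE=IND), and no new data. P values are larger and intervals wider on average, not in every dataset. By √DE − 1, widening is about 2-9% at ICC 0.05 (√1.045 to √1.193) and 4-47% at ICC 0.1-0.3 (√1.09 to √2.157).

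For 30% vs 12% at mean 0.9, Poisson counts and ICC 0.1, simulated power is 0.74 for the clustered test against 0.77 for chi-square. The loss is larger with overdispersion and high ICC. Part of the chi-square advantage comes from its inflated alpha.

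Clustering on patient does not address confounding between the non-randomised groups or differences between the two colonoscopists.
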